10.4.3 Analysis of the Secondary Endpoint(s)

All secondary efficacy analyses will be performed based on the ITT analysis set.

Overall Response Rate (ORR)

Overall response rate is defined as the proportion of randomized subjects who achieve a best response of PR or better using modified IMWG criteria ([Appendix 2](#)).

Overall response rate will be compared between arms using a stratified Cochran Mantel-Haenszel (CMH) chi-square test with a two-sided $\alpha = 0.05$ level. The response rate, along with its exact two-sided 95% CI, will be computed within each treatment group. A two-sided 95% CI for difference of response rate between the treatment groups will also be computed.

A sensitivity analysis of ORR may be conducted by excluding those subjects who already began treatment with Dara IV prior to Amendment 1.

Very Good Partial Response (VGPR) or Better Rate, CR or Better Rate, MRD Negativity Rate

Very good partial response (VGPR) or better rate is defined as the proportion of randomized subjects who achieve a best response of VGPR or better using modified IMWG criteria.

Complete response (CR) or better rate is defined as the proportion of randomized subjects who achieve a best response of CR or better using modified IMWG criteria.

Minimal residual disease (MRD) negativity rate is defined as the proportion of randomized subjects who achieve a negative result of MRD. Subjects without MRD assessment will be considered as having MRD-positive results.

These categorical endpoints will be analyzed similarly to ORR.

Time to Response

Time to response is defined for subjects who achieve a confirmed response as the time between the date of randomization and the first efficacy evaluation that the subject has met all criteria for PR or better.

Descriptive statistics will be used to summarize time to response.

Duration of Response (DoR)

Duration of response will be restricted to the randomized subjects who achieve a best response of PR or better. It is measured from the time, in months, that the criteria for response are first met until the date of a progression event (according to the primary definition of PFS). A subject with response who does not have a progression event will be censored at the same time they were censored under the primary definition of PFS.

The DoR for each treatment group will be estimated descriptively using the Kaplan-Meier product-limit method.

Time to Next Therapy

Time to next therapy will be defined as the time, in months, from the date of randomization to the date of subsequent antimyeloma therapy or death from any cause, whichever comes first. For subjects who neither start a new antimyeloma therapy nor die, survival time will be censored at the date of their last available follow-up date. For a randomized subject who does not have any post-baseline follow-up assessments and who has not died, survival time will be censored at the randomization date.

Time to next therapy will be analyzed similarly to PFS.

Overall Survival (OS)

Overall survival is defined as the time, in months, from the date of randomization to the date of death from any cause. If a subject is not known to have died, survival time will be censored at the date of last contact (“last known date alive”). Overall survival will be analyzed similarly to PFS.

Patient Reported Outcomes Measures

EORTC QLQ-C30, EORTC QLQ-MY20 scale and single-item scores, and EQ-5D-5L visual analog scale and utility values will be summarized at each time point. Treatment effect will be assessed by change from baseline at each time point summarized by treatment group.

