7.1 STUDY PROCEDURES/EVALUATIONS

7.1.1 Efficacy Assessments

The primary endpoint of this study is PFS. Secondary efficacy endpoints are OS, ORR, DoR, and time to next therapy.

Response or disease progression will be assessed by the investigator for treatment decision based on the analysis of serum and urine protein electrophoresis (SPEP and UPEP), serum and urine immunofixation (sIFE and uIFE), serum free light chain protein (sFLC), imaging and bone marrow assessments, per modified IMWG guidelines ([Appendix 2](#)). The statistical analysis will use derived response or disease progression based on a validated computer algorithm that has been shown to provide consistent review of the data necessary to determine disease progression and response according to the modified IMWG criteria.

All efficacy laboratory assessments will be collected locally and analyzed centrally unless otherwise indicated in [Table 7.1](#). The disease assessments SPEP, UPEP, and serum calcium corrected for albumin should be collected every cycle for the first 14 months of the study and every other month thereafter. After Cycle 1, IFE should only be done when endogenous M-protein is 0 or nonquantifiable. For subjects who are followed by FLC only, these assessments are performed every other cycle after 14 months. If the subject does not have documented disease progression as defined in [Appendix 2](#) at the time of study drug discontinuation, then disease assessments must continue to be performed according to the same schedule

shown in *Table 7.3* until disease progression even if a subsequent anti-myeloma treatment is started prior to disease progression:

- Laboratory analysis for response assessment (SPEP, UPEP, sIFE, uIFE, sFLC)
- Minimal Residual Disease analysis for subjects with suspected CR or better performed by next-generation sequencing according to *Table 7.1* and the Schedule of Events (*Table 7.3*)
- Daratumumab-specific Immunofixation Electrophoresis (DSIFE) for subjects with IgGκ sub-type achieving VGPR or better

The following assessments will be carried out at local laboratory, if available, or at the Erasmus laboratory:

- Cytogenetics by means of Fluorescence In Situ Hybridization (FISH) at study entry

Disease assessments will be collected locally and analyzed centrally unless otherwise indicated in *Table 7.1*.

Table 7.1: Disease assessment

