Based on modified IMWG criteria, response must be confirmed for all categories other than SD in order to rule out errors. A consecutive assessment can be performed at any time and confirmation should be obtained by M-protein assessments.

- Bone marrow assessments do not need to be repeated, but at least 1 bone marrow assessment is required to substantiate a CR.
- If imaging studies were done, they need to rule out new lytic bone lesions.
- Should confirmation assessments reveal a better category (eg, VGPR after PR), the response category of the previous assessment will be considered as confirmed (PR).
- Should confirmation assessments reveal a worse category, (eg, VGPR after CR), the response category of the subsequent assessment will be considered as confirmed (VGPR).
- Should repeated measurements of a variable result in more values, the worst assessment is to be considered.

Laboratory Confirmation of Progressive Disease

A diagnosis of PD requires confirmation if determined based on M-protein measurement or serum FLC levels. Confirmation of an increase in M-protein or FLC should be obtained as soon as possible.

See [Section 7.1.1.3](#) for information concerning possible false protein electrophoresis (PEP) and immunofixation (IFE) results.

Sponsor Confirmation of Progressive Disease

A diagnosis of PD (that is also confirmed with a consecutive assessment if based on M-protein/serum FLC levels) must be reported, via email, to the Sponsor's Medical Reviewer within 1 working day using the Progressive Disease Notification Form together with all supporting documentation for the diagnosis. The Medical Reviewer will check that the investigator's assessment of PD is consistent with the IMWG criteria and will provide a confirmation on the same form and return it via email to the site. In the case that the investigator's assessment is not deemed consistent with the IMWG criteria, the Medical Reviewer will

provide comments in the relevant section of the notification form and may also contact the investigator to discuss the subject further.

Study treatment discontinuation and start of subsequent anti-myeloma therapy should occur only after Sponsor confirmation of PD.

For subjects continuing on the study after the positive primary analysis and final OS analysis, investigator assessment of PD should continue to be performed in accordance with IMWG criteria. Notification of PD and approval by the Sponsor is no longer required.

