7.2.3 Follow-up Period

Post-treatment Follow-up

Subjects who discontinue treatment for reasons other than documented disease progression, death, lost to follow-up, or withdrawal of consent should continue to be followed for response assessments every 4 weeks as in [Table 7.3](#). The reason for completion/discontinuation should be recorded on the eCRF.

If a subject starts new anti-myeloma therapy prior to disease progression, every attempt should be made to perform tumor evaluations until documented disease progression. In addition, all new anti-neoplastic therapy administered starting from the last dose of the study treatment until death, lost to follow-up, or withdrawal of consent will be recorded in the eCRFs.

Survival Follow-up

Subjects will be followed every 12 weeks, or more frequently, after disease progression for survival and subsequent myeloma therapy.

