10.4.2 Analysis of the Primary Efficacy Endpoint(s)

The efficacy analysis will be performed based on the ITT analysis set.

Progression Free Survival (PFS)

Progression free survival is defined as the time, in months, from the date of randomization to the date of the first documented disease progression or death due to any cause, whichever comes first. Clinical deterioration will not be considered progression. For subjects who neither progress nor die, the PFS time will be censored at the date of their last adequate disease assessment. For subjects who start a new anti-MM treatment, PFS time will be censored at the date of last adequate assessment before the start of the new treatment. For a randomized subject who does not have any post-baseline disease assessments and who has not died, PFS time will be censored at the randomization date.

Progression free survival will be compared between treatment groups using a stratified log-rank test with a one-sided $\alpha = 0.025$ level. The distribution of PFS for each treatment group will be estimated using the Kaplan-Meier product-limit method. Median and two-sided CIs for median PFS will be computed by treatment group. Kaplan-Meier plots of PFS will be presented.

A stratified Cox proportional hazard model for PFS with treatment arm as single factor will be used to estimate the HR of DaraPomDex to PomDex and its corresponding 95% CI. The stratification factor will be the same as that used in the randomization process.

Absolute frequencies and proportions of subject with disease progression or all-cause death will also be provided.

A sensitivity analysis of PFS may be conducted by excluding those subjects who already began treatment with Dara IV prior to Amendment 1.

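### Does Section 10.4.3 need a written cut-off so that responses first reached on the next myeloma regimen do not count?

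*Combined protocol and SAP*

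**What the plan says.** Section 10.4.3 defines the main response endpoint without a time limit: "Overall response rate is defined as the proportion of randomized subjects who achieve a best response of PR or better using modified IMWG criteria". VGPR or better and CR or better also rest on best response, MRD negativity on a negative result, and time to response on the first evaluation meeting PR or better. None mentions subsequent therapy.

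The time-to-event endpoints do. Under Section 10.4.2, for a subject who starts new treatment, "PFS time will be censored at the date of last adequate assessment before the start of the new treatment". DoR inherits that date. Its clock is described as follows: "It is measured from the time, in months, that the criteria for response are first met until the date of a progression event". A responder without such an event "will be censored at the same time they were censored under the primary definition of PFS".

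Data after a switch will exist. Section 7.1.1 continues assessments "until disease progression even if a subsequent anti-myeloma treatment is started prior to disease progression", and Section 7.2.3 adds: "If a subject starts new anti-myeloma therapy prior to disease progression, every attempt should be made to perform tumor evaluations until documented disease progression".

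Early switching is nevertheless restricted. Section 7.1.1 says: "Study treatment discontinuation and start of subsequent anti-myeloma therapy should occur only after Sponsor confirmation of PD". After the primary analysis, Section 7.2.4 and footnote 16 of Table 7.3 drop Sponsor approval but still require IMWG progression before new therapy. Table 7.3 does not permit other anti-neoplastic therapy during treatment.

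The only PFS sensitivity analysis named is optional and concerns route of administration: "A sensitivity analysis of PFS may be conducted by excluding those subjects who already began treatment with Dara IV prior to Amendment 1".

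**The concern.** The response endpoints and PFS appear to follow different rules for the same event. A subject who switches without progressing leaves the PFS risk set at the last assessment before the switch. That subject stays under observation for response, and nothing in Section 10.4.3 stops a later PR from counting.

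Three things would be at stake.

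- **Confirmatory tests.** ORR, VGPR or better, CR or better and MRD negativity are four of the five secondary endpoints under type I error control (Section 10.4.9). The trial is open-label, so switching could differ by arm, and the numerators would then include an effect of the next regimen.
- **Coherence of DoR.** If PFS is censored at month 5 and the first PR comes at month 8, DoR is 5 - 8 = -3 months.
- **PFS.** Censoring at the switch is informative if subjects switch because they are about to progress. No PFS analysis named in Section 10.4.2 uses the assessments made after the switch.

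**Working it through.** **Design figures.** Schoenfeld's formula with HR 0.621, one-sided 0.025, 90% power and 1:1 allocation gives 4 × (1.960 + 1.282)² / (ln 0.621)² = 186 events, against 188 stated. Power at 188 events is 90.4%. Allowing for 7% early censoring, 280 / 0.93 = 301.1, or 302 subjects when rounded to equal arms of 151. The plan's figures reproduce, and none depends on the point at issue.

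**Who is affected.** Set the definitions side by side:

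- A first PR after the switch affects ORR and time to response, and DoR becomes negative.
- A PR before the switch that deepens afterwards can affect VGPR, CR or MRD. DoR still starts at the earlier PR and is not negative.

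So the negative DoR is confined to first responses after the switch.

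**Size for ORR.** Inputs from the documents are 31% for PomDex (Section 2.2), 59% for DaraPomDex (Section 2.1.2) and 151 per arm (Section 10.5). Two assumptions are added. The share *s* of non-responders who switch before progression is 7%, borrowed from the allowance for all permanent early censoring. The response rate *r* on the next regimen is 30% or 60%. The rate under the literal reading is p + (1 - p) × s × r.

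- PomDex: 0.31 + 0.69 × 0.07 × 0.3 = 32.4%; with *r* = 0.6, 33.9%. That is 2.2 to 4.4 extra responders of 151.
- DaraPomDex: 0.59 + 0.41 × 0.07 × 0.3 = 59.9%; with *r* = 0.6, 60.7%. That is 1.3 to 2.6 extra responders.

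| Who switches | ORR difference (28.0 points with no switching) | Power, two-sided 0.05 |
|---|---|---|
| Both arms | 27.4 to 26.8 | 99.8% |
| PomDex only | 26.6 to 25.1 | 99.7 to 99.4% |
| DaraPomDex only | 28.9 to 29.7 | 99.9 to 99.96% |

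With no switching, power is 99.9%. Shifts in VGPR, CR and MRD were not computed. MRD and CR should move less, because on-study marrow is sampled only from suspected CR onward.

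**Size for PFS.** This was simulated with exponential times, a 24-month cutoff and assumed control medians of 4 to 10 months. The stated share of each arm's progressors is censored one month before progression, which is fully informative and so a worst case.

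| Progressors censored, PomDex / DaraPomDex | Estimate when true HR is 0.62 | Estimate when true HR is 1.00 |
|---|---|---|
| 7% / 7% | 0.62 | 1.00 |
| 10% / 5% | 0.65 | 1.05 |
| 5% / 10% | 0.59 | 0.95 |

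In the second row, 81-98% of PomDex subjects progress by 24 months, so about 8-10% of that arm is censored. That is more than the 7% the plan allows for all early censoring.

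**The case for a change.** The strongest case for acting is that a confirmatory numerator should not depend on an unstated programming choice. Section 10.4.3 defines these endpoints itself and does not defer their window to the SAP. Even a deliberate decision to count responses whatever the therapy would not rescue the text, because DoR would still take the PFS censoring date. The ORR result is also reassuring partly because the illustrative effect is large. With an assumed DaraPomDex rate of 46%, and 5-15% of non-responders switching in PomDex alone, power falls from 76.6% to between 70.3% and 34.0%.

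The silence is real, and one written sentence would have been better. The rest carries less weight. The incompatibility with DoR itself shows which reading is intended: only a window ending at the PFS date makes the definitions fit together, and a single negative duration would expose any other choice in programming checks. The fall to 34.0% combines an effect size not found in the documents, one-sided switching at more than twice the 7% allowance, and a 60% response rate on the next regimen. It also requires adopting the literal reading. Switching in PomDex alone would work against the experimental arm. The opposite imbalance would favour it, but by only 0.9 to 1.7 points at 7%.

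On PFS, unequal informative switching can move the estimate by about 0.03 at the planned effect and 0.05 at the null. That justifies interest in a supplementary analysis. It does not make an explicit and conventional censoring rule wrong.

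**Conclusion.** No change is needed. Section 10.4.3 leaves a detail unwritten that analysts settle in the ordinary way: best response, MRD negativity, time to response and the start of DoR are taken from assessments up to the PFS event or censoring date. No passage says that later responses count, and status is derived by a validated algorithm (Sections 7.1.1 and 10.1). Its specification and a separate SAP are not in the document reviewed and may already state the window.

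Even under the literal reading, the illustrative ORR difference moves by at most 2.9 points (28.0 to 25.1) with power above 99%. This rests on the cited historical response rates, 7% switching and 30-60% response on the next regimen. The conclusion is less secure for a much smaller ORR effect with heavy one-sided switching, and VGPR, CR and MRD were not quantified. DoR and time to response are descriptive and outside the error-controlled family.

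A PFS analysis that ignores subsequent therapy could be run from data already collected, but it is optional and corrects no error. Timing points the same way. The current text is Amendment 5 of March 2024, and Table 7.3 dates the primary cutoff to 21 July 2020. Rewriting controlled response definitions now, or adding a PFS analysis to Section 10.4.2, would be post hoc.

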2.2 RATIONALE

Synergistic combinations that target various mechanisms to overcome drug resistance need to be examined in order to realize daratumumab's full potential. To this end, daratumumab is being investigated as part of multidrug chemotherapy regimens. The cytotoxicity induced by the anti-CD38 antibody, together with the immunomodulatory effects of pomalidomide, could represent an important and effective anti-myeloma combination therapy.

Clinical studies have demonstrated the efficacy and safety of combining daratumumab with bortezomib and with lenalidomide. Apart from the daratumumab infusion reactions, which can be minimized with premedication, AEs in these studies were similar to those reported in studies of either bortezomib or lenalidomide alone. Since lenalidomide and pomalidomide are in the same drug class and have a similar

safety and pharmacokinetic profile, the addition of daratumumab to pomalidomide should give rise to a similar safety profile as did the lenalidomide - daratumumab combination.

Pomalidomide is an option for patients who have relapsed/refractory MM and who live in the US, the EU, or elsewhere that pomalidomide has a marketing authorization. The FDA granted accelerated approval for pomalidomide based on a Phase 2 study of subjects with relapsed and refractory disease after at least 2 prior regimens, including lenalidomide and bortezomib. Subjects received either pomalidomide alone (n=108) or in combination with 40 mg/week dexamethasone (n=113) ([Richardson et al 2014](#)). With a median follow-up of 14.2 months, median PFS was 4.2 and 2.7 months (HR=0.68; p = 0.003); ORR (\geq PR) was 33% vs. 18% (p=.013); median response duration was 8.3 vs. 10.7 months; and median OS was 16.5 vs. 13.6 months, respectively for the pomalidomide + dexamethasone arm compared with the pomalidomide alone arm. The most common hematologic Grade 3 or 4 AEs were neutropenia (41% vs. 48%), anemia (22% vs. 24%), and thrombocytopenia (19% vs. 22%), respectively for the pomalidomide + dexamethasone vs. pomalidomide alone arm. The most common non-hematologic AEs were pneumonia (22% vs. 15%) and fatigue (14% vs. 11%) in the pomalidomide + dexamethasone arm compared with the pomalidomide alone arm, respectively.

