3.2 SECONDARY OBJECTIVES

The secondary objectives of the study are the following:

- To compare ORRs between treatment arms.
- To compare DoR between treatment arms.
- To compare time to next therapy between treatment arms.
- To compare OS between treatment arms.
- To assess the safety and tolerability of the investigational combination treatment.
- To assess the depth of response by analyzing MRD negativity rate for CR or better and for suspected CR/sCR.
- To compare health-related quality-of-life (HRQoL) and health utility between treatment arms.
- To evaluate the immunomodulatory effects of daratumumab on T cells.
- To evaluate daratumumab pharmacokinetics and immunogenicity and the immunogenicity of rHuPH20.

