10.4.9 Multiple Comparison/Multiplicity

Unless stated otherwise, one-sided alpha level 0.025 will be considered. Strong control of family-wise Type I error rate will be controlled at a one-sided significance level of 0.025 for the following major secondary endpoints: OS, ORR, VGPR or better rate, CR or better rate, and MRD negativity rate. A hierarchical testing procedure will be used. Details about this procedure will be specified in the SAP for this study.

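### Duration of response is to be compared between arms, but the only stated analysis is a descriptive curve per arm among responders, which is not a randomized comparison

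*Combined protocol and SAP*

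**What the plan says.** The Protocol Summary and Section 3.2 both list as a secondary objective: "To compare DoR between treatment arms".

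Section 10.4.3 opens its secondary analyses with a general rule: "All secondary efficacy analyses will be performed based on the ITT analysis set". For DoR it then narrows the set: "Duration of response will be restricted to the randomized subjects who achieve a best response of PR or better". Duration runs from the time response criteria are first met to a progression event under the primary PFS definition, with PFS censoring otherwise. The method is one sentence: "The DoR for each treatment group will be estimated descriptively using the Kaplan-Meier product-limit method". No hazard ratio, test, interval for a difference, or version over all randomized subjects is given.

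The other comparative efficacy objectives do get a contrast. ORR has a stratified CMH test and a confidence interval for the difference. Time to next therapy and OS are analyzed like PFS.

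Section 10.4.9 confines family-wise error control to these "major secondary endpoints: OS, ORR, VGPR or better rate, CR or better rate, and MRD negativity rate". DoR is not among them.

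**The concern.** The objective asks for a comparison, and the plan supplies two curves that do not carry one. Randomization makes the arms comparable as assigned. It does not make the responders of one arm comparable with the responders of the other when treatment affects who responds. A longer or shorter curve in the DaraPomDex arm could reflect a drug effect on duration, a different mix of responders, or both, and the curves alone cannot separate these.

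A reader who takes the objective at its word will read the two medians as a treatment effect. That reading could understate, overstate or reverse the effect on time spent in response. No success claim rests on DoR, so what is at stake is the interpretation of a named secondary objective, not the trial's primary conclusion.

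**Working it through.** **How unequal the responder groups could be.** The plan gives no size or power figure for DoR, so the starting point is its number per arm. Section 10.5 has 280 evaluable subjects and 7% early censoring: 280 / 0.93 = 301.1, rounded up to an even 302, or 151 per arm. This reproduces.

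Background response rates, taken as assumptions:

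- DaraPomDex 59% (single-arm phase 1b study, Section 2.1.2): 151 × 0.59 = 89.1
- PomDex 31% (phase 3 study, Section 2.2): 151 × 0.31 = 46.8

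About 89 versus 47 subjects would enter the curves. The other PomDex rates in Section 2.2, 29.4% and 33%, give 44.4 and 49.8, so the control count runs from about 44 to 50.

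**What the cited randomized phase 2 study shows.** Section 2.2 compares pomalidomide plus dexamethasone (n=113) with pomalidomide alone (n=108). Combination first:

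| Measure | Combination | Alone | Ratio |
|---|---|---|---|
| ORR | 33% | 18% | 1.83 |
| Median PFS, months | 4.2 | 2.7 | 1.56 |
| Median OS, months | 16.5 | 13.6 | 1.21 |
| Median response duration, months | 8.3 | 10.7 | 0.78 |

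In the protocol's words, "median response duration was 8.3 vs. 10.7 months". It is the only one of the four that favors the single agent.

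**Could that be chance?** The protocol gives no interval for this difference. Responders number about 113 × 0.33 = 37 and 108 × 0.18 = 19. Assuming exponential durations, the hazard ratio is 10.7 / 8.3 = 1.29. Even if every responder had an event, the standard error of its log is √(1/37 + 1/19) = 0.282. The 95% CI is exp(0.254 ± 1.96 × 0.282), about 0.74 to 2.24, with z = 0.254 / 0.282 = 0.90. Censoring would widen it. Chance is a sufficient explanation.

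**The same study counted over everyone randomized.** With exponential durations and non-responders at 0, mean time in response is ORR × median / ln 2:

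- Combination: 0.33 × 8.3 / 0.693 = 3.95 months
- Alone: 0.18 × 10.7 / 0.693 = 2.78 months

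The ratio is 1.42, in the same direction as ORR, PFS and OS. This illustrates how the population changes the answer. It has no time horizon, so it is not a value of the restricted measure proposed below.

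**This trial's own regimens.** Section 2.1.2 gives DaraPomDex an ORR of 59% and a median DoR of 13.6 months. Section 2.2 gives PomDex 33% and 8.3 months. Here DoR and ORR point the same way (13.6 / 8.3 = 1.64; 59 / 33 = 1.79). The comparison is across studies, and the 13.6-month median was reported at 9.8 months of median follow-up, so it sets an expectation and no more.

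**The case against.** The best defense is that the plan is already cautious. It calls the DoR analysis descriptive, attaches no test or hazard ratio, and keeps DoR out of the hierarchy. A log-rank test among responders would be worse, because it would put a p-value on a selected comparison. PFS, ORR, time to next therapy and OS are all compared as randomized, and Section 10.4.10 leaves further exploratory analyses to the SAP. All of this stands, and it keeps the point small. It does not supply an answer to the stated objective. PFS runs from randomization whether or not a subject responds, and ORR ignores duration, so neither measures time in response. The deferrals in the text reviewed cover the testing hierarchy, subgroups and unspecified exploratory work. None promises a DoR measure over all randomized subjects.

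The objection is also right about stronger readings. From the phase 2 figures a reader might infer that responder selection has been shown at work, that daratumumab will add harder-to-treat responders, or that DoR will reverse in this trial. The documents support none of these. The study added dexamethasone, not daratumumab. Its DoR difference rests on about 37 and 19 responders and is compatible with chance. Nothing describes how long additional responders on daratumumab would stay in response. The figures for the two regimens under study point the other way.

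**Conclusion.** The point holds as a mismatch between objective and analysis: the plan promises a comparison of DoR and specifies only a responder-only description. The curves would rest on about 89 versus 47 of 151 subjects if the background response rates apply. Their difference has no randomized interpretation, and the direction of any distortion is unknown. A result that runs against PFS and ORR is possible but not predicted.

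The conclusion that the comparison is not randomized needs only that treatment affects response, which the plan itself expects by testing ORR. The counts depend on the assumed response rates; the phase 2 calculations depend on exponential durations. This is a cheap improvement to a secondary analysis. The PFS analysis and error control are unaffected.

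**What to change.** Keep the responder-only Kaplan-Meier DoR and label it descriptive and not a randomized comparison.

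Answer the objective in the ITT set with restricted mean time in response, measured from randomization to a fixed horizon that follow-up supports in both arms, with non-responders counted as 0. Compute it per arm as the area, up to the horizon, between two Kaplan-Meier curves: PFS, and time to first response, progression or death. Use the same censoring rules for both. Report the between-arm difference with a 95% bootstrap CI, resampling subjects within arm, and assign it no alpha. State in the SAP how the horizon is chosen.

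The cost is a paragraph of SAP text and one supportive analysis on response and progression dates already collected. The downside is a measure less familiar to readers than median DoR. If the sponsor does not want it, the minimum repair is to reword the objective so that it describes DoR by arm instead of comparing it; that removes the mismatch but leaves the comparative question unanswered.
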